Sample Size Rationale

The sample size was chosen to provide an appropriate long-term safety database. It is not based on statistical hypothesis.

Schedule of Assessments

Assessment	Visit 1 Screening and Baseline	Visit 2, 3, 4 and 5 (Months 1, 3, 6 and 9)	Visit 6/EoS/ ET¹
Obtain informed consent/HIPAA	X		
Review inclusion / exclusion criteria	X		
Review migraine history, medical history and concomitant medications	X		
MIDAS questionnaire	X	X	X
Review resource utilization (visits to specialists, ERs, etc.)	X	X	X
Complete physical examination	X		
Vital signs (heart rate, blood pressure)	X ²	X	X
Brief physical examination based on AE(s)	X ²	X	X
Weight	X		X
12-lead ECG	X ³	VISIT 4 ONLY	X
Clinical laboratory ⁴	X ³	VISIT 2 and 4	X
Urine pregnancy for women of child-bearing potential	X ^{5,6}	X ⁶	X ⁶
Columbia Suicide Severity Rating Scale	X ³	X	X
Randomization	X		
Dispense study drug, study diary, and provide detailed instructions	X	X	
Collect empty dosing card(s) and unused study drug. Review dosing compliance and diary		X	X
Migraine attack (electronic diary) documentation by subject		X	
Documentation of rescue/recurrence medication		X	X
Documentation of adverse events and concomitant		X	X

1. **ET** is for subjects that discontinue the study between scheduled visits. The patient should return to the clinic within 14 days of the decision to withdraw from the study. **EoS** is the designation for any scheduled visit that the subject discontinues at or Visit 6 (month 12).
2. Brief physical examination based on AE (s) and vital signs will be the values obtained from **EoS/Visit 2** of COL MIG-301 or COL MIG-302 only if subject signs consent and enrolls in COL MIG-305 on the same day.
3. Laboratory tests, ECG and C-SSRS will be the values obtained from **EoS/Visit 2** of COL MIG-301 or COL MIG-302, as long as the subject signs consent and enrolls in COL MIG-305 on the same day or within two weeks (14 days) of **EoS/Visit 2**.
4. Clinical laboratory tests include hematology, biochemistry, lipid profile and urinalysis. In the event of clinically significant laboratory findings, including but not limited to hepatic laboratory abnormalities, repeat or additional laboratory testing may be required outside of a scheduled clinic visit.
5. A urine pregnancy test for women of childbearing potential is required unless Visit 1 is same day as EoS/Visit 2 of COL MIG-301 or COL MIG-302.

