9.1.5.2 Abnormal and Clinically Significant Results

The Investigator must categorize all abnormal hematology, chemistry, and urinalysis laboratory values as either CS or NCS. Clinical significance is defined as any variation in laboratory parameters, which has medical consequences that result in an alteration in the subject's medical care. The Investigator will use the WHO Toxicity Criteria (see Appendix 1) as a guide when evaluating the clinical significance of all abnormal clinical laboratory results. In case of CS laboratory results, the Investigator will continue to monitor the subject with additional laboratory assessments until (1) values have reached normal range and/or baseline levels, or (2) the Investigator has judged that the abnormal values are not related to the administration of study drug or other protocol-specific procedures.

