9.1.5.3 Hepatic Safety Monitoring

If a study subject experiences elevated ALT $\geq 3X$ ULN, AST $\geq 3X$ ULN, ALP $\geq 2X$ ULN, or elevated TBL $\geq 2X$ ULN, liver testing (Appendix 5) should be repeated within 3 to 5 days including ALT, AST, ALP, TBL, direct bilirubin, gamma-glutamyl transferase, and creatine kinase to confirm the abnormality and to determine if it is increasing or decreasing. If the abnormality persists or worsens, clinical and laboratory monitoring should be initiated by the investigator and in consultation with the study medical monitor. Monitoring of ALT, AST, TBL, and ALP should continue until levels normalize or return to approximate baseline levels.

Hepatic Safety Data Collection

Additional safety data should be collected if 1 or more of the following conditions occur:

- Elevation of serum ALT to $\geq 5X$ ULN on 2 or more consecutive blood tests
- Elevation of serum AST to $\geq 5X$ ULN on 2 or more consecutive blood tests
- Elevated serum TBL to $\geq 2X$ ULN (except for cases of known Gilbert's syndrome)
- Elevation of serum ALP to $\geq 2X$ ULN on 2 or more consecutive blood tests
- Subject discontinued from treatment due to a hepatic event or abnormality of liver tests
- Hepatic event considered to be a SAE

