## **12.2 Clinical Laboratory Evaluation**

Laboratory results will be classified based on the reference ranges provided by the central laboratory.

For quantitative laboratory parameters, observed and change from baseline measurements will be presented by time point using descriptive statistics. Categorical urinalysis parameters will only be presented in a listing. Laboratory parameters will be presented in standards international (SI) units.

Shift tables describing out-of-reference range shifts will be provided for clinical laboratory test results, as appropriate by treatment group and dose based on the laboratory parameters as described below.

For each parameter, the out-of-reference range shifts will be classified as:

- Low
- Normal
- High

Shifts will be presented for lowest post baseline results and for highest post baseline results for all described laboratory parameters.

Laboratory blood data and urine data will be collected during **Screening/Visit 1 (ONLY** if more

than two weeks since **EoS/Visit 2** of COL MIG-301 or COL MIG-302) and at visit **Month 1/Visit 2, Month 6/Visit 4, and Month 12/Visit 6/EoS/ET**. If **Screening/Visit 1** is the same day the data will be used for both parent and Gladiator studies. In that case the baseline for this data will be considered from parent study (301 or 302) where subject was randomized previously, and respective lab parameters will be mapped by subject for new study for analysis. If **Screening/Visit 1** is within 2 weeks of **EoS/Visit 2** of COL MIG-301 or COL MIG-302 the data obtained will be used for both studies except a urine pregnancy test for WOCBP will be performed separately. In that case data for urine analysis will be used from current study. The question “When did the subject enter 305?” from CRF will be used to determine when the screening/Visit 1 for each subject was performed.

In the case of repeated laboratory values at the same visit, the last value collected will be used for the analysis.

Additionally, plots of ALT and AST vs. Total bilirubin by treatment group will also be produced, with reference lines at 3xULN for ALT, AST, and 2XULN for Total bilirubin. In each plot, Total bilirubin will be in the vertical axis.

The following laboratory parameters will be summarized:

- Hematology
  - White blood cell (WBC) count with differential (neutrophils, lymphocytes, eosinophils, monocytes, basophils),
  - hemoglobin,
  - hematocrit,
  - platelet count,
  - red blood cell (RBC) count

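### SAP 12.2 keeps the last repeated laboratory value at a visit and does not exempt the lowest/highest post-baseline shift tables, so a more extreme value can drop out of the summaries

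*SAP*

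**What the plan says.** SAP 12.2 sets one rule for repeats: "In the case of repeated laboratory values at the same visit, the last value collected will be used for the analysis". It refers to the analysis as a whole and names no output to which it does not apply.

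The same section plans three kinds of output:
- by-visit observed values and changes from baseline;
- low/normal/high shift tables, for which "Shifts will be presented for lowest post baseline results and for highest post baseline results for all described laboratory parameters";
- liver plots: "plots of ALT and AST vs. Total bilirubin by treatment group will also be produced, with reference lines at 3xULN for ALT, AST", with a second line at 2xULN for bilirubin. The text does not say whether each subject's maximum, each visit's value or every value is plotted.

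The protocol makes repeat testing depend on the result. Under Protocol 9.1.5.2, a clinically significant result is followed until "values have reached normal range and/or baseline levels", or until the investigator judges it unrelated to study drug or procedures. Under Protocol 9.1.5.3, after a liver elevation the tests "should be repeated within 3 to 5 days including ALT, AST, ALP, TBL", the stated purpose being "to confirm the abnormality and to determine if it is increasing or decreasing". If the abnormality persists or worsens, follow-up goes on: "Monitoring of ALT, AST, TBL, and ALP should continue until levels normalize or return to approximate baseline levels". Footnote 4 of the protocol's Schedule of Assessments adds that "repeat or additional laboratory testing may be required outside of a scheduled clinic visit". The SAP's own copy of that footnote (SAP 2.1) lacks this sentence.

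**The concern.** A highest-value or lowest-value table exists to show the worst result a subject had on treatment. Choosing the last of several values at a visit before taking the extreme works against that purpose, because follow-up usually runs until the result has come back towards normal. If the triggering value and its repeats share a visit label, the value carried forward tends to be the recovered one.

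Scheduled post-baseline blood is drawn only at Months 1, 6 and 12 (Protocol 5.4), so each scheduled sample is one of three planned chances to see an abnormality. Long-term safety is the study's primary objective. Shift tables and liver plots are where a reader of a study of about 2580 planned subjects would look for a laboratory signal. An error that always makes those outputs look cleaner deserves to be closed even if it turns out to be small.

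**Working it through.** The documents give no figure to reproduce. The question is what the rule does to the worst-value outputs.

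**Direction.** Let a subject's values at visit v be x(v,1), ..., x(v,n), in order of collection. The rule keeps x(v,n). Since x(v,n) ≤ max over i of x(v,i) at every visit, the highest post-baseline value under the rule is never above the true highest. By the same argument the lowest is never below the true lowest. The effect is zero or an understatement.

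**Invented series, in multiples of ULN** (not trial data):
- ALT: Visit 2 0.8; Visit 4 4.0, repeats 2.0 and 0.9; Visit 6 0.8.
- Bilirubin: Visit 2 0.5; Visit 4 2.2, repeats 1.2 and 0.6; Visit 6 0.5.

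| Handling | Highest ALT | Highest bilirubin |
|---|---|---|
| Repeats recorded under Visit 4, last-value rule | max(0.8, 0.9, 0.8) = 0.9 | max(0.5, 0.6, 0.5) = 0.6 |
| Repeats recorded as unscheduled, last-value rule | 4.0 (Visit 4 value stays) | 2.2 (Visit 4 value stays) |
| Maximum of all post-baseline values | 4.0 | 2.2 |

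In the first row the subject is classed Normal. In the other two the subject is High and lies beyond both reference lines, if subject maxima are what is plotted.

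**A worsening repeat.** For ALT 3.2 at Visit 4 and 5.0 on repeat, the last-value rule keeps 5.0 if both sit under Visit 4, which is correct. If the repeat is unscheduled and unscheduled samples are left out of the extreme, the table shows 3.2. The SAP does not say whether such samples enter.

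**Range of possible size.** Let N = 2580 (planned enrolment, Protocol synopsis), r = the share of subjects with a qualifying elevation, and s = the share of those whose normalising repeats carry the same visit label with no other abnormal visit. Subjects shown = N × r × (1 − s). Both r and s are assumptions; neither document gives them.

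| r | Subjects with elevation (N × r) | s = 0 | s = 25% | s = 50% | s = 100% |
|---|---|---|---|---|---|
| 0.5% | 12.9 | 12.9 | 9.7 | 6.5 | 0 |
| 1% | 25.8 | 25.8 | 19.4 | 12.9 | 0 |
| 2% | 51.6 | 51.6 | 38.7 | 25.8 | 0 |

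The number lost therefore runs from none to all, and s decides it. N is planned enrolment, not dosed subjects with a post-baseline sample, so these counts are upper illustrations.

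**Comparison within the SAP.** For ECG (12.4) and physical examination (12.5) the SAP takes the worst post-baseline value and writes no last-value rule. Laboratory data are handled differently, and no reason is given.

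**The case against.** The strongest reply is that the rule covers only repeats at the same visit. A hepatic repeat is taken 3 to 5 days later and may be outside a scheduled visit, so on an ordinary reading it is a separate collection and the Visit 2, 4 or 6 value is untouched. This stands as a limit on size. It does not settle the matter, because SAP 12.2 names only Visits 1, 2, 4 and 6 for laboratory data, has no convention for assigning repeats to visits, and does not say whether unscheduled values count towards the extremes.

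A second reply is that the shift-table sentence is the specific one and the last-value sentence merely picks one record per visit for the descriptive summaries. That is a sensible intention, but the text does not express it.

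Further points stand in part:
- Values are not lost from the report. SAP 12 lists all safety values, and Protocol 10.5.2 flags out-of-range and clinically significant ones.
- Some abnormalities surface elsewhere, as adverse events (Protocol 9.2.1) or through additional hepatic data collection (Protocol 9.1.5.3). The bilirubin of 2.2xULN in the invented series would trigger the latter. A single ALT rise below 5xULN with normal bilirubin need not, and the laboratory example of an adverse event requires that a medical intervention was started.
- Laboratory parameters are additional safety endpoints (SAP 3.4), summarised descriptively. The primary endpoint is adverse-event proportions.
- The hepatic repeat section came with the latest protocol amendment, so it may cover only part of the study. The general follow-up rule in 9.1.5.2 is not among that amendment's changes.

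A reader might infer that any liver abnormality repeated until it normalises is certain to vanish from the tables and plots. The documents do not support that. Visit labelling is not stated, the plotted value is undefined, follow-up under 9.1.5.2 can end with an abnormal value judged unrelated, and an equally abnormal result at another visit would still show.

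**Conclusion.** The point holds in conditional form. As written, the last-value rule reaches the lowest/highest post-baseline shift tables. Whenever a less extreme repeat is recorded under the triggering visit and no other visit is as extreme, the more extreme value drops out of the table. The liver plots may be affected too, but that is an inference until the SAP defines what is plotted.

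The direction is certain for the extreme-value tables: understatement or no effect. The size cannot be derived from the documents. It is zero if all repeats are recorded as unscheduled and the scheduled value is used. It could reach every resolved abnormality if all repeats carry the triggering visit's label. The loss is from the summaries only.

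This should be fixed, but it does not threaten the primary analysis. Confidence is medium: high for the conflict between the rule and the extreme-value tables, low for the number of subjects affected.

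**What to change.** Amend SAP 12.2 as follows:
1. Limit the last-value rule to the by-visit descriptive summaries.
2. Base the lowest and highest post-baseline shifts on the minimum and maximum of all post-baseline values, including repeats and unscheduled samples.
3. Base the ALT/AST versus bilirubin plots on the maximum of all post-baseline values in the same way, and state whether the two coordinates must come from the same sample.
4. State how repeat and unscheduled samples are assigned to visits, so that the by-visit summaries are reproducible.

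Items 2 and 3 give the same extremes however repeats are labelled, so they do not depend on item 4. They also bring laboratory data into line with the worst-value approach already used for ECG and physical examination.

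The cost is a short SAP change and a revised worst-value flag in the laboratory dataset, with no new samples. Reported abnormality rates may come out slightly less favourable. Because SAP 5.6 intends the same tables at the final lock as at the May 2018 lock, the same rule should apply to both, or the difference should be stated.

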### 12.3 Vital Signs

Observed and change from baseline values for vital sign measurements will be summarized for the following parameters:

- Systolic blood pressure (mmHg)
- Diastolic blood pressure (mmHg)
- Heart rate (bpm)
- Weight (lb)

Vital signs data will be collected during **Screening/Visit 1** and at visits **Month 1/Visit 2**, **Month 6/Visit 4**, and **Month 12/Visit 6/EoS/ET**. If **Screening/Visit 1** is the same day the data will be used for both parent and Gladiator studies. In that case the baseline for this data will be considered from parent study (301 or 302) where subject was randomized previously, and respective vitals parameters will be mapped by subject for new study for analysis. The question “When did the subject enter 305?” from CRF will be used to determine when the screening/Visit 1 for each subject was performed.

Additionally subjects with categorical changes of interest in SBP, DBP, weight and heart rate will be summarized in frequencies and percentages based on the baseline categories in the same table of Appendix 16.3.

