- Time to headache relief and time to pain free after a second dose of lasmiditan for rescue or recurrence of migraine
- MBS free after a second dose of lasmiditan for rescue or recurrence of migraine
- Total number of migraine attacks and attacks treated with study medication over each 3 month

period

Resource utilization:

- Any CV events and/or related resource utilization such as visits to cardiologists, procedures, hospitalizations, new treatments or treatment adjustments for CV disease as collected in study COL MIG-301 or COL MIG-302 compared to on study **Visit 1** through **Visit 6/EoS/ET**.
- Any visits to an emergency room or physician's office for treatment of migraine as collected in study COL MIG-301 or COL MIG-302 compared to on study **Visit 1** through **Visit 6/EoS/ET** excluding study specific visits.
- Concomitant medications for the treatment of migraine and/or pain as collected in study COL MIG-301 or COL MIG-302 compared to concomitant medications for migraine and/or pain **Visit 1** through **Visit 6/EoS/ET**.
- Missed days of work and/or school or daily activities based on responses to MIDAS questionnaire.

Statistical Analysis:

Safety:

Adverse events will be summarized in terms of the proportion of patients and the proportion of attacks associated with any adverse event and with specific adverse events. Physical examinations, vital signs, clinical laboratory parameters (hematology, serum chemistry and urinalysis) and ECG parameters will be summarized in terms of change from baseline status at 1, 3, 6, 9 and 12 months or early termination.

Efficacy:

This is an open-label study with no control group. Efficacy data will be summarized using descriptive statistics. The proportion of attacks treated with study medication which respond at 2 hours will be calculated for each 3 month period.

Resource Utilization:

Resource utilization such as visits to cardiologists, procedures, hospitalizations, new treatments or treatment adjustments for CV disease as well as visits to the emergency room or a physician's office for the treatment of migraine will be summarized by treatment arm in terms of patient reported information recorded in study COL MIG-301 or COL MIG-302 compared to information reported at **Visits 2, 3, 4, 5, and EoS/ET/6**. Concomitant medication use for migraine and/or pain and missed days of work and/or school or daily activities based on responses to MIDAS questionnaire will be summarized by treatment arm.

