9.1.3 Vital Signs

Vital signs, measured after at least 5 minutes rest, will include seated systolic blood pressure (SBP), diastolic blood pressure (DBP) and heart rate (HR). All vital sign measurements will be

performed by appropriately qualified and authorized study personnel, using appropriate equipment.

Blood pressure (BP) will be measured after at least 5 minutes rest and if possible in the same arm at each visit by using an automated sphygmomanometer. The results will be recorded in millimeters of mercury (mmHg). HR will be measured in the radial artery in the dominant arm for 30 seconds and will be recorded as beats per minute (bpm).

Vital signs will be assessed at **Screening/Visit 1** and at **Month 1/Visit 2, Month 3/Visit 3, Month 6/Visit 4, Month 9/Visit 5** and **Month 12/Visit 6/EoS/ET**. If **Screening/Visit 1** is the same day as **EoS/Visit 2** of COL MIG-301 or COL MIG-302 the vital signs obtained will be used for both studies.

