Subjects will be asked to return to the clinic at months 1, 3, 6, 9 and 12 (Visits 2, 3, 4, 5 and 6). At each visit a brief physical examination based on adverse events (AEs), vital signs and a urine pregnancy test on all WOCBP will be obtained. Blood and urine samples for clinical laboratory parameters (hematology, serum chemistry and urinalysis) will be obtained at **Month 1/Visit 2**, **Month 6/Visit 4** and **Month 12/Visit 6 (EoS/ET)**. A 12-lead ECG will be obtained at **Month 6/Visit 4** and **Month 12/Visit 6 (EoS/ET)**. C-SSRS will be completed at each visit. The MIDAS questionnaire will be completed at **Month 1/Visit 2**, **Month 3/Visit 3**, **Month 6/Visit 4**, **Month 9/Visit 5** and **Month 12/Visit 6 (EoS/ET)**. At each visit, resource utilization, AEs, use of concomitant medication, use of study drug and subject diary compliance will be assessed; subjects who are continuing will be dispensed study drug. Subjects who decide to withdraw at a scheduled visit should confirm the date of the visit is 7 days ( $\pm$  2 days) from their last migraine treated with study drug. Subjects who decide to discontinue between scheduled visits are asked to contact the clinic to schedule an **ET /Visit 6** within two weeks (14 days) after discontinuation of dosing. Subjects may be discontinued if more than one month of no migraine(s) treated with study drug is reported. The total time on study is up to 54 weeks (a maximum of 378 days).

This study is designed to evaluate the safety and tolerability of long-term intermittent use of lasmiditan 100 mg and of lasmiditan 200 mg, as the first dose and as a second dose, for the acute treatment of migraine.

The study will be conducted at up to 180 centers in US and ex-US (all Study 301/LAHJ or Study 302/LAHK centers will be included).

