**Schedule of Assessments**

	Visit 1 Screening and Baseline	Visit 2, 3, 4 and 5 (Months 1, 3, 6 and 9)	Visit 6/EoS/ ET1
Obtain informed consent/HIPAA		X	
Review inclusion / exclusion criteria		X	
Review migraine history, medical history and concomitant medications		X	
MIDAS questionnaire	X	X	X
Review resource utilization (visits to specialists, ERs, etc.)	X	X	X
Complete physical examination		X	
Vital signs (heart rate, blood pressure)	X 2	X	X
Brief physical examination based on AE(s)	X 2	X	X
Weight		X	X
12-lead ECG	X 3	VISIT 4 ONLY	X
Clinical laboratory 	X 3	VISIT 2 and 4	X
Urine pregnancy for women of child-bearing potential	X 5,6	X 6	X 6
Columbia Suicide Severity Rating Scale	X 3	X	X
Randomization		X	
Dispense study drug, study diary, and provide detailed instructions		X	X
Collect empty dosing card(s) and unused study drug.		X	X
Review dosing compliance and diary completion			
Migraine attack (electronic diary) documentation by subject		X	
Documentation of rescue/recurrence medication		X	X
Documentation of adverse events and concomitant medication		X	X

**ET** is for subjects that discontinue the study between scheduled visits. The subject should return to the clinic within 14 days of the decision to withdraw from the study. **EoS** is the designation for any scheduled visit that the subject discontinues at or Visit 6 (month 12).

2. Brief physical examination based on AE (s) and vital signs will be the values obtained from **EoS/Visit 2** of COL MIG-301 or COL MIG-302 only if subject signs consent and enrolls in COL MIG-305 on the same day.

3. Laboratory tests, ECG and C-SSRS will be the values obtained from **EoS/Visit 2** of COL MIG-301 or COL MIG-302, as long as the subject signs consent and enrolls in COL MIG-305 on the same day or within two weeks (14 days) of **EoS/Visit 2**.

4. Clinical laboratory tests include hematology, biochemistry, lipid profile and urinalysis.

5. A urine pregnancy test for women of childbearing potential is required unless **Visit 1** is same day as **EoS/Visit 2** of COL MIG-301 or COL MIG-302.

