**16.3 CRITERIA FOR CATEGORICAL CHANGES OF INTEREST IN VITAL SIGNS (SBP, DBP, PULSE, WEIGHT)**

Parameter	Direction	Criteria	Subjects Population defined by Baseline Categories
Systolic BP (mm Hg)(sitting)	Low	≤90 and decrease ≥20	All Subjects; >90; ≤90
	High	≥140 and increase ≥20	All Subjects; <140; ≥140
	PCS High	≥180 and increase ≥20	All Subjects; <180; ≥180
	Sustained Elevation	≥140 and increase ≥20 at 2 consecutive visits	All Subjects; <140; ≥140
Diastolic BP (mm Hg) (sitting)	Low	≤50 and decrease ≥10	All Subjects; >50; ≤50
	High	≥90 and increase ≥10	All Subjects; <90; ≥90
	PCS High	≥105 and increase ≥15	All Subjects; <105; ≥105
	Sustained Elevation	≥90 and increase ≥10 at 2 consecutive visits	All Subjects; < 90; ≥90
Systolic BP or Diastolic BP (mm Hg) (sitting)	Sustained Elevation	Meeting criteria for systolic BP for 2 consecutive visits or meeting criteria for diastolic BP for 2 consecutive visits or both	All Subjects
Pulse (bpm) (sitting)	Low	<50 and decrease ≥15	All Subjects; ≥50; <50

	High	>100 and increase $\geq 15$	All Subjects; $\leq 100$ ; >100
	Sustained Elevation	>100 and increase $\geq 15$ at 2 consecutive visits	All Subjects; $\leq 100$ ; >100
Weight (lb)	Low	(Loss) decrease $\geq 7\%$	All Subjects
	High	(Gain) increase $\geq 7\%$	All Subjects

Abbreviations: BP = blood pressure; PCS = potentially clinically significant; mm Hg = millimeters of mercury; bpm = beats per minute.

Note, “all subjects” include all subjects in safety population with at least 1 non-missing baseline and at least 1 postbaseline measure.

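### SAP 12.3 lists vital signs at Months 1, 6 and 12 only, against the protocol and the SAP's own schedule; if followed in analysis, the sustained-elevation category would rest on readings 5–6 months apart

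*SAP*

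**What the plan says.** The visit list in SAP 12.3 opens with "Vital signs data will be collected during" and in full reads: "Vital signs data will be collected during Screening/Visit 1 and at visits Month 1/Visit 2, Month 6/Visit 4, and Month 12/Visit 6/EoS/ET". Months 3 and 9 are absent. The section then calls for observed and change-from-baseline summaries of systolic and diastolic pressure, heart rate and weight, and for the categorical changes defined in Appendix 16.3.

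Four other places give a fuller schedule:

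- Protocol 9.1.3: "Vital signs will be assessed at Screening/Visit 1 and at Month 1/Visit 2, Month 3/Visit 3, Month 6/Visit 4, Month 9/Visit 5", followed by the Month 12/EoS/ET visit.
- Protocol synopsis, Statistical Analysis. The sentence that covers vital signs ends: "ECG parameters will be summarized in terms of change from baseline status at 1, 3, 6, 9 and 12 months or early termination".
- SAP 2.1: "At each visit a brief physical examination based on adverse events (AEs), vital signs and a urine pregnancy test", in the paragraph that sets the visits at Months 1, 3, 6, 9 and 12.
- SAP schedule of assessments. The vital-signs row is marked for Visits 2 to 5 without restriction, whereas the same column limits ECG to Visit 4 and laboratory tests to Visits 2 and 4.

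Appendix 16.3 defines sustained elevation of systolic pressure as "≥140 and increase ≥20 at 2 consecutive visits" and of diastolic pressure as "≥90 and increase ≥10 at 2 consecutive visits", with a parallel rule for pulse. It does not say what makes two visits consecutive.

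Protocol section 10 requires changes to the analysis methods to be described and justified in the SAP. SAP 5.1, which lists such changes, says nothing about vital-sign visits.

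**The concern.** Section 12.3 is the operative analysis section for vital signs, so a programmer would reasonably look there for the visits. Read on its own, its list seems deliberate, because SAP 12.5, 12.6 and 13 each name all five post-baseline visits for their own data.

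Most of the consequence falls on the sustained-elevation category. Its meaning depends on which visits count as neighbours, and the only visit list in 12.3 puts the neighbours five or six months apart. Blood pressure and heart rate matter in this study: protocol section 4 says the data will be used to confirm safety in patients with cardiovascular risk factors, and SAP 4.1 plans a subgroup on those factors.

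**Working it through.** The documents give no detection rate for sustained elevation, so there is no planned figure to reproduce. They also give no frequency, onset or duration of blood pressure rises. The models in steps 3 and 4 are therefore assumptions, and none of the steps allows for dropout.

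**Step 1. Pairs available.**

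- Full schedule (Months 1, 3, 6, 9, 12): four pairs, 1–3, 3–6, 6–9 and 9–12, with gaps of 2, 3, 3 and 3 months.
- SAP 12.3 list (Months 1, 6, 12): two pairs, 1–6 and 6–12, with gaps of 5 and 6 months.
- Readings dropped: 2 of 5.

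**Step 2. Enumeration, with no onset model.** Five visits give 4 + 3 + 2 + 1 = 10 unbroken runs of two or more elevated visits. The full schedule detects all 10. The short list misses 5: the four two-visit runs (1–3, 3–6, 6–9, 9–12) and the run 3–6–9. A rise present from Month 1 to Month 12 is never missed.

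Across all 2^5 = 32 patterns of elevated and normal visits, the full schedule flags 19 and the short list flags 12, with 9 in common. The 3 flagged only by the short list are elevation at Months 1 and 6 alone, at 6 and 12 alone, and at 1, 6 and 12 alone. In each, every adjacent scheduled pair includes a normal reading.

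**Step 3. One rise, onset uniform on 0–12 months, duration D.** A pair (a, b) detects the rise if onset lies between max(0, b − D) and a. The detection probability is the length of the union of these windows divided by 12.

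- D = 4. Full: [0,1], [2,3], [5,6], [8,9], so 4/12 = 33%. Short: no window, 0%.
- D = 6. Full: the windows cover [0,9], so 9/12 = 75%. Short: [0,1] only, 1/12 = 8%.
- D = 9. Full: 9/12 = 75%. Short: [0,1] and [3,6], 4/12 = 33%.
- Persistent. Full: [0,9], 75%. Short: [0,6], 6/12 = 50%.

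For D from 6 to 11 months, full detection stays at 9/12 and short-list detection is (D − 5)/12. The share of full-schedule detections that is missed is 1 − (D − 5)/9. This gives 89% at 6 months, 56% at 9 and 33% at 11 months or longer. It crosses one half at D = 9.5.

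**Step 4. Independent chance p of meeting the criterion at each visit, q = 1 − p.**

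- Full: 1 − (q^5 + 5pq^4 + 6p²q³ + p³q²).
- Short: 2p² − p³.
- Short but not full: 2p²q³ + p³q².

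| p | Full | Short | Share of full detections missed | Share of short-list flags failing the full rule |
|---|---|---|---|---|
| 0.1 | 3.7% | 1.9% | 90% | 81% |
| 0.5 | 59.4% | 37.5% | 53% | 25% |
| 0.9 | 98.7% | 89.1% | 11% | 1% |

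Where the criterion is met only sporadically, the two lists flag largely different subjects.

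**The case against.** The strongest reply is that the sentence in 12.3 describes collection, which the protocol governs. The sentences in 12.3 that describe the summaries name no visits. Appendix 16.3 takes in any subject with a baseline and at least one post-baseline value, and SAP section 12 promises listings of all safety values, so the Month 3 and 9 readings would at least be listed. The same short list appears in 12.2, where it is right for laboratory tests, and in 12.4, where it implies a Month 1 ECG that the schedule does not contain. It also fits weight badly, since protocol 9.1.2 and SAP 12.5 measure weight only at Visit 1 and Visit 6/EoS/ET. Carry-over from the laboratory section is plausible, though the documents cannot prove it.

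This reply stands to the extent that a reader might infer that the SAP uses only Months 1, 6 and 12, and no text says so. It does not remove the contradiction. A list that is probably accidental can still be programmed as written, and nothing in 12.3 or 16.3 tells the programmer otherwise.

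It is also fair that the High and potentially clinically significant categories in 16.3 need no second visit. They could lose readings under the short list but have no pairing problem.

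**Conclusion.** The visit list in SAP 12.3 is wrong as written. It conflicts with the protocol's collection schedule, the protocol's planned summaries and two places in the SAP, and the SAP does not declare it as a change. If it governs the analysis, sustained elevation needs readings 5–6 months apart and misses every rise seen at just two adjacent scheduled visits.

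Two stronger readings are tempting, and the documents do not support them:

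- That most sustained rises would be missed. By enumeration exactly half of the runs are missed. Under uniform onset, more than half are missed only for rises shorter than about 9.5 months; for persistent rises the loss is one third.
- That the safety conclusion is biased toward no effect. In both models the short list flags fewer subjects overall, so the main loss is sensitivity. It also flags subjects who were normal at a skipped visit, so the error is partly misclassification. Sustained elevation is one descriptive category and not the primary endpoint.

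The mismatch can be read directly from the documents. The size depends on the list being followed, on no dropout and, for the percentages, on the assumed onset or per-visit models. An early leaver's EoS/ET reading would change the available pairs. The point should be corrected, but it does not threaten the primary adverse-event analysis.

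**What to change.** - **SAP 12.3:** list Months 1, 3, 6, 9 and 12/EoS/ET for blood pressure and heart rate. List weight separately at Visit 1 and Visit 6/EoS/ET.
- **SAP 16.3:** define consecutive as adjacent scheduled visits on that five-visit schedule, and add a rule for missed, unscheduled and ET visits.
- **SAP 12.4:** reconcile the ECG visit list with the schedule, which has no Month 1 ECG.
- **Existing tables:** SAP 5.6 has the final lock repeat the May 2018 tables, so confirm which visits those vital-sign tables used.

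The cost is SAP wording and a programming check. The protocol already collects the Month 3 and 9 readings, so no new data or protocol amendment is needed.
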